## 12. CHANGES IN THE CONDUCT OF THE STUDY OR PLANNED ANALYSIS

The cold symptoms' duration was defined in the protocol as the number of symptomatic days between D1 and the first day the subject reports not having the symptom for two consecutive days.

Furthermore, since several patients still reported having symptoms while they reported they did not feel sick anymore at the question 1 during the two last days of completion of the WURSS-21 questionnaire, their positive answers to the cold symptoms' items have been considered as non-significant. Consequently, the question 1 has been taken into account instead of the corresponding items to determine the end of the cold symptoms' duration, however only on the condition that the two last days of completion were consecutive.

If the two last days of completion were not consecutive, positive answers to cold symptoms' items are still considered as symptomatic, even if the two last answers to the question 1 are negative. The symptom ends at the last symptomatic day if the patient reported the absence of this symptom after this day. Otherwise, the duration of the symptom is censored at D15 or at the end of the study, whichever occurs first.

## 13. APPENDICES

### 13.1. List of statistical tables, figures and listings

Type	Number	Title
STUDY SUBJECTS		
Table	14.1.1.1	Subjects' disposition – Screened subjects
Listing	14.1.1.1	Not included / excluded subjects – Reasons – Screened subjects
Figure	14.1.1.1	Subjects' disposition – Screened subjects
Table	14.1.1.2.1	Summary of protocol deviations by category and type – Included subjects
Listing	14.1.1.2.1	Subjects with at least one protocol deviation – Included subjects
Table	14.1.1.2.2	Premature withdrawal – Reason of withdrawal
Listing	14.1.1.2.2	Subjects prematurely withdrawn – Included subjects
DEMOGRAPHIC AND OTHER BASELINE CHARACTERISTICS, COMPLIANCE, STUDY DURATION		
Table	14.1.2.1	Demographic characteristics – Safety Set
Table	14.1.2.2	Summary of previous and concomitant medications at baseline – Safety Set
Table	14.1.2.3	Medical and surgical past history – Safety Set
Table	14.1.2.4	Symptoms of acute infectious rhinitis at baseline – Safety Set
Table	14.1.2.5	Total WURSS-21 score at baseline – Safety Set
Table	14.1.2.6	Results of the COVID-19 antigen test at baseline – Safety Set
Table	14.1.3	Summary of compliance per treatment group – Safety Set
Table	14.1.4	Study duration by subject – Safety Set
EFFICACY		
Table	14.2.1.1	AUC on total WURSS-21 score per treatment group – Full Analysis Set
Table	14.2.1.2	AUC on total WURSS-21 score per treatment group – Per-Protocol Set
Figure	14.2.1.1	Boxplots of AUC on total WURSS-21 score by treatment group – Full Analysis Set
Figure	14.2.1.2	Boxplots of AUC on total WURSS-21 score by treatment group – Per-Protocol Set
Table	14.2.2.1.1	AUC for each of the WURSS-21 components (symptoms and Quality-of-Life) scores per treatment group – Full Analysis Set
Table	14.2.2.1.2	AUC for each of the WURSS-21 components (symptoms and Quality-of-Life) scores per treatment group – Per-Protocol Set
Figure	14.2.2.1.1	Boxplots of AUC on symptoms' and Quality-of-Life's WURSS-21 scores by treatment group – Full Analysis Set

Type	Number	Title
Figure	14.2.2.1.2	Boxplots of AUC on symptoms' and Quality-of-Life's WURSS-21 scores by treatment group – Per-Protocol Set
Table	14.2.2.2	Impact of the treatment on the cold symptoms' duration – Full Analysis Set
Figure	14.2.2.2	Boxplots of the cold symptoms' durations by treatment group – Full Analysis Set
Table	14.2.2.3.1	Number of days of use of concomitant treatments that may affect common cold symptoms in each group – Full Analysis Set
Table	14.2.2.3.2	Number of days of use of antipyretics in each group – Full Analysis Set
Table	14.2.2.3.3	Number of days of use of systemic/local mucolytics in each group – Full Analysis Set
Table	14.2.2.3.4	Number of days of use of decongestants in each group – Full Analysis Set
Table	14.2.2.3.5	Number of days of use of antitussives in each group – Full Analysis Set
Table	14.2.2.3.6	Number of days of use of antibiotics in each group – Full Analysis Set
Table	14.2.2.4	Subject general satisfaction in each group – Full Analysis Set
Table	14.2.3	Concomitant treatments – Full Analysis Set
Table	14.2.4.1.1	Summary of non-related adverse events – Safety Set
Table	14.2.4.1.2	Non-related treatment-emergent adverse events by System Organ Class and Preferred Term – Safety Set
Listing	14.2.4.2.1	Listing of non-related adverse events leading to definitive discontinuation of the trial device – Safety Set (if applicable)
Listing	14.2.4.2.2	Listing of non-related adverse events leading to definitive discontinuation of the study – Safety Set (if applicable)

**SAFETY – INCIDENTS**

Table	14.3.1.1	Summary of incidents – Safety Set
Table	14.3.1.2	Related treatment-emergent adverse events by System Organ Class and Preferred Term – Safety Set
Listing	14.3.2.1	Listing of serious incidents – Safety Set (if applicable)
Listing	14.3.2.2	Listing of incidents leading to definitive discontinuation of the trial device – Safety Set (if applicable)
Listing	14.3.2.3	Listing of incidents leading to definitive discontinuation of the study – Safety Set (if applicable)

**SUBJECTS DATA LISTINGS**

Listing	16.2.1.1	Subjects discontinued from the study after enrolment
Listing	16.2.2.1	Subjects with protocol deviations
Listing	16.2.3.1	Subjects' disposition and analysis sets

Type	Number	Title
Listing	16.2.4.1	Demographic characteristics by subject
Listing	16.2.4.2	Medical history by subject
Listing	16.2.4.3	Symptoms of acute infectious rhinitis
Listing	16.2.4.4	Inclusion/Exclusion criteria
Listing	16.2.5.1	Dates of visits
Listing	16.2.5.2	Compliance to Healsea Rescue intake
Listing	16.2.6.1	Questionnaire WURSS-21
Listing	16.2.6.2	Previous and concomitant medications by subject
Listing	16.2.6.3	Patients' satisfaction questionnaire
Listing	16.2.7.1	Adverse events, incidents and expected side effects
Listing	16.2.8.1	COVID-19 antigen tests

[figure not shown]
## 13.2. Mock tables

**Table 14.1.1.1. Subjects' disposition – Screened subjects**

	Healsea Rescue N=XX	Placebo N=XX	Total N=XX
Analysis Sets			
Screened subjects	XX (100.0%)	XX (100.0%)	XX (100.0%)
Included subjects	XX ( XX.X%)	XX ( XX.X%)	XX ( XX.X%)
Randomised subjects	XX ( XX.X%)	XX ( XX.X%)	XX ( XX.X%)
Safety Set	XX ( XX.X%)	XX ( XX.X%)	XX ( XX.X%)
Full Analysis Set	XX ( XX.X%)	XX ( XX.X%)	XX ( XX.X%)
Per-Protocol Set	XX ( XX.X%)	XX ( XX.X%)	XX ( XX.X%)

**Listing 14.1.1.1. Not included / excluded subjects – Reasons – Screened subjects**

ID – Sex – Age	Category	Inclusion / Exclusion criterion	Answer
	Inclusion		No
	Exclusion		Yes

**Figure 14.1.1.1. Subjects' disposition – Screened subjects**

**Table 14.1.1.2.1. Summary of protocol deviations by category and type – Included subjects**

Category of deviation – Type of deviation	Healsea Rescue N=XX	Placebo N=XX	Total N=XX
Subjects with at least one protocol deviation			
All	XX (XX.X%)	XX (XX.X%)	XX (XX.X%)
Major deviations			
All	XX (XX.X%)	XX (XX.X%)	XX (XX.X%)
XXXXX	XX (XX.X%)	XX (XX.X%)	XX (XX.X%)
XXXXX	XX (XX.X%)	XX (XX.X%)	XX (XX.X%)
Minor deviations			
All	XX (XX.X%)	XX (XX.X%)	XX (XX.X%)
XXXXX	XX (XX.X%)	XX (XX.X%)	XX (XX.X%)
XXXXX	XX (XX.X%)	XX (XX.X%)	XX (XX.X%)

**Listing 14.1.1.2.1. Subjects with at least one protocol deviation – Included subjects**

ID – Sex – Age	Treatment	Safety Set	Full Analysis Set	Per-Protocol Set	Protocol deviation	Classification of deviation

**Table 14.1.1.2.2. Premature withdrawal – Reason of withdrawal**

	Healsea Rescue N=XX	Placebo N=XX	Total N=XX
Reason of premature withdrawal			
XXXXXXX	XX (XX.X%)	XX (XX.X%)	XX (XX.X%)

**Listing 14.1.1.2.2. Subjects prematurely withdrawn – Included subjects**

ID – Sex – Age	Treatment	Safety Set	Full Analysis Set	Per-Protocol Set	Reason of withdrawal

**Table 14.1.2.1. Demographic characteristics – Safety Set**

	Healsea Rescue N=XX	Placebo N=XX	Total N=XX
Age (years)			
N	XX	XX	XX
Missing	XX	XX	XX
Mean (SD)	XX.X (XX.X)	XX.X (XX.X)	XX.X (XX.X)
Median	XX	XX	XX
Q1/Q3	XX / XX	XX / XX	XX / XX
Min/Max	XX / XX	XX / XX	XX / XX
Sex			
N	XX	XX	XX
Missing	XX	XX	XX
Female	XX (XX.X%)	XX (XX.X%)	XX (XX.X%)
Male	XX (XX.X%)	XX (XX.X%)	XX (XX.X%)

**Table 14.1.2.2. Summary of previous and concomitant medications at baseline – Safety Set**

ATC1 - ATC2	Healsea Rescue N=XX	Placebo N=XX	Total N=XX
Subjects with at least one previous medication			
All	XX (XX.X%)	XX (XX.X%)	XX (XX.X%)
XXXXX			
All	XX (XX.X%)	XX (XX.X%)	XX (XX.X%)
XXXXX	XX (XX.X%)	XX (XX.X%)	XX (XX.X%)
XXXXX	XX (XX.X%)	XX (XX.X%)	XX (XX.X%)

**Table 14.1.2.3. Medical and surgical past history – Safety Set**

SOC - Preferred Term	Healsea Rescue N=XX	Placebo N=XX	Total N=XX
Subjects with at least one medical history			
All	XX (XX.X%)	XX (XX.X%)	XX (XX.X%)
XXXXX			
All	XX (XX.X%)	XX (XX.X%)	XX (XX.X%)
XXXXX	XX (XX.X%)	XX (XX.X%)	XX (XX.X%)
XXXXX	XX (XX.X%)	XX (XX.X%)	XX (XX.X%)

**Table 14.1.2.4. Symptoms of acute infectious rhinitis at baseline – Safety Set**

	Healsea Rescue N=XX	Placebo N=XX	Total N=XX
XXXXX score			
N	XX	XX	XX
Missing	XX	XX	XX
Mean (SD)	XX.X (XX.X)	XX.X (XX.X)	XX.X (XX.X)
Median	XX	XX	XX
Q1/Q3	XX / XX	XX / XX	XX / XX
Min/Max	XX / XX	XX / XX	XX / XX
Between-groups test	XXX (Student/Wilcoxon)		
Total score			
N	XX	XX	XX
Missing	XX	XX	XX
Mean (SD)	XX.X (XX.X)	XX.X (XX.X)	XX.X (XX.X)
Median	XX	XX	XX
Q1/Q3	XX / XX	XX / XX	XX / XX
Min/Max	XX / XX	XX / XX	XX / XX
Between-groups test	XXX (Student/Wilcoxon)		

**Table 14.1.2.5. Total WURSS-21 score at baseline – Safety Set**

	Healsea Rescue N=XX	Placebo N=XX	Total N=XX
Total WURSS-21 score			
N	XX	XX	XX
Missing	XX	XX	XX
Mean (SD)	XX.X (XX.X)	XX.X (XX.X)	XX.X (XX.X)
Median	XX	XX	XX
Q1/Q3	XX / XX	XX / XX	XX / XX
Min/Max	XX / XX	XX / XX	XX / XX
Between-groups test	XXX (Student/Wilcoxon)		

**Table 14.1.2.6. Results of the COVID-19 antigen test at baseline – Safety Set**

	Healsea Rescue N=XX	Placebo N=XX	Total N=XX
COVID-19 antigen test			
N	XX	XX	XX
Missing	XX	XX	XX
Negative	XX (XX.X%)	XX (XX.X%)	XX (XX.X%)
Positive	XX (XX.X%)	XX (XX.X%)	XX (XX.X%)
Between-groups test	XXX (Chi-2/Fisher)		

**Table 14.1.3. Summary of compliance per treatment group – Safety Set**

	Healsea Rescue N=XX	Placebo N=XX	Total N=XX
Compliance (%)			
N	XX	XX	XX
Missing	XX	XX	XX
Mean (SD)	XX.X (XX.X)	XX.X (XX.X)	XX.X (XX.X)
Median	XX	XX	XX
Q1/Q3	XX / XX	XX / XX	XX / XX
Min/Max	XX / XX	XX / XX	XX / XX

**Table 14.1.4. Study duration by subject – Safety Set**

	Healsea Rescue N=XX	Placebo N=XX	Total N=XX
Study duration (days)			
N	XX	XX	XX
Missing	XX	XX	XX
Mean (SD)	XX.X (XX.X)	XX.X (XX.X)	XX.X (XX.X)
Median	XX	XX	XX
Q1/Q3	XX / XX	XX / XX	XX / XX
Min/Max	XX / XX	XX / XX	XX / XX

**Table 14.2.1.2. AUC on total WURSS-21 score per treatment group – Per-Protocol Set**

[figure not shown]
	Healsea Rescue N=XX	Placebo N=XX	Total N=XX
AUC on total WURSS-21 score			
N	XX	XX	XX
Missing	XX	XX	XX
Mean (SD)	XX.X (XX.X)	XX.X (XX.X)	XX.X (XX.X)
Median	XX	XX	XX
Q1/Q3	XX / XX	XX / XX	XX / XX
Min/Max	XX / XX	XX / XX	XX / XX
Between-groups test	XXX (Student/Wilcoxon)		

**Table 14.2.2.1.2. AUC for each of the WURSS-21 components (symptoms and Quality-of-Life) scores per treatment group – Per-Protocol Set**

	Healsea Rescue N=XX	Placebo N=XX	Total N=XX
AUC on symptoms' WURSS-21 score			
N	XX	XX	XX
Missing	XX	XX	XX
Mean (SD)	XX.X (XX.X)	XX.X (XX.X)	XX.X (XX.X)
Median	XX	XX	XX
Q1/Q3	XX / XX	XX / XX	XX / XX
Min/Max	XX / XX	XX / XX	XX / XX
Between-groups test	XXX (Student/Wilcoxon)		
AUC on Quality-of-Life's WURSS-21 score			
N	XX	XX	XX
Missing	XX	XX	XX
Mean (SD)	XX.X (XX.X)	XX.X (XX.X)	XX.X (XX.X)
Median	XX	XX	XX
Q1/Q3	XX / XX	XX / XX	XX / XX
Min/Max	XX / XX	XX / XX	XX / XX
Between-groups test	XXX (Student/Wilcoxon)		

**Table 14.2.2.1. Impact of the treatment on the cold symptoms' duration – Full Analysis Set**

	Healsea Rescue N=XX	Placebo N=XX
XXX – Duration (days)		
N	XX	XX
Missing	XX	XX
Mean (SD)	XX.X (XX.X)	XX.X (XX.X)
Median [95%CI]	XX.X [XX.X; XX.X]	XX.X [XX.X; XX.X]
Q1/Q3	XX / XX	XX / XX
Min/Max	XX / XX	XX / XX
p-value (Wilcoxon)	XXX	

**Figure 14.2.X.X. Boxplots of XXX by treatment group – XXX Set**

**Table 14.2.2.3.X. Number of days of use of XXX in each group – Full Analysis Set**

	Healsea Rescue N=XX	Placebo N=XX
Number of days of intakes of XXX		
N	XX	XX
Missing	XX	XX
0	XX.X (XX.X%)	XX.X (XX.X%)
1	XX.X (XX.X%)	XX.X (XX.X%)
2	XX.X (XX.X%)	XX.X (XX.X%)
...	XX.X (XX.X%)	XX.X (XX.X%)
Between-groups test	XXX (Chi-2/Fisher)	

**Table 14.2.2.4. Subject general satisfaction in each group – Full Analysis Set**

	Healsea Rescue N=XX	Placebo N=XX
How would you characterize the use of the nasal spray?		
N	XX	XX
Missing	XX	XX
Not easy	XX (XX.X%)	XX (XX.X%)
Pretty easy	XX (XX.X%)	XX (XX.X%)
Easy	XX (XX.X%)	XX (XX.X%)
Very easy	XX (XX.X%)	XX (XX.X%)
Between-groups test	XXX (Chi-2/Fisher)	
How would you characterize the residual taste after spraying the prescribed treatment?		
N	XX	XX
Missing	XX	XX
Not pleasant	XX (XX.X%)	XX (XX.X%)
Neutral	XX (XX.X%)	XX (XX.X%)
Pleasant	XX (XX.X%)	XX (XX.X%)
Very pleasant	XX (XX.X%)	XX (XX.X%)
Between-groups test	XXX (Chi-2/Fisher)	
How would you characterize the cleansing and moistening of nasal mucosa with the prescribed treatment?		
N	XX	XX
Missing	XX	XX
No improvement	XX (XX.X%)	XX (XX.X%)
Slight improvement	XX (XX.X%)	XX (XX.X%)
Moderate improvement	XX (XX.X%)	XX (XX.X%)
Very clear improvement	XX (XX.X%)	XX (XX.X%)
Between-groups test	XXX (Chi-2/Fisher)	
Will you recommend the prescribed treatment for treatment of acute rhinitis?		
N	XX	XX
Missing	XX	XX
No	XX (XX.X%)	XX (XX.X%)
Yes	XX (XX.X%)	XX (XX.X%)
Between-groups test	XXX (Chi-2/Fisher)	

**Table 14.2.3. Concomitant treatments – Full Analysis Set**

ATC1 - ATC2	Healsea Rescue N=XX	Placebo N=XX	Total N=XX
Subjects with at least one concomitant medication			
All	XX (XX.X%)	XX (XX.X%)	XX (XX.X%)
XXXXXX			
All	XX (XX.X%)	XX (XX.X%)	XX (XX.X%)
XXXXXX	XX (XX.X%)	XX (XX.X%)	XX (XX.X%)
XXXXXX	XX (XX.X%)	XX (XX.X%)	XX (XX.X%)

**Table 14.2.4.1.1. Summary of non-related adverse events – Safety Set**

	Healsea Rescue N=XX			Placebo N=XX		
	n (%)	[E]	n (%)	[E]	n (%)	[E]
Number and percentage of subjects with non-related / Number of non-related						
Adverse event	XX (XX.X%)	XXX	XX (XX.X%)	XXX	XX (XX.X%)	XXX
Adverse event leading to definitive study device discontinuation	XX (XX.X%)	XXX	XX (XX.X%)	XXX	XX (XX.X%)	XXX
Adverse event leading to definitive study discontinuation	XX (XX.X%)	XXX	XX (XX.X%)	XXX	XX (XX.X%)	XXX
Treatment-emergent adverse event	XX (XX.X%)	XXX	XX (XX.X%)	XXX	XX (XX.X%)	XXX

**Table 14.2.4.1.2. Non-related treatment-emergent adverse events by System Organ Class and Preferred Term – Safety Set**

SOC - Preferred Term	Healsea Rescue N=XX			Placebo N=XX		
	n (%)	[E]	n (%)	[E]	n (%)	[E]
Non-related treatment-emergent adverse events						
All	XX (XX.X%)	XXX	XX (XX.X%)	XXX	XX (XX.X%)	XXX
XXXXXX						
All	XX (XX.X%)	XXX	XX (XX.X%)	XXX	XX (XX.X%)	XXX
XXXXXX	XX (XX.X%)	XXX	XX (XX.X%)	XXX	XX (XX.X%)	XXX
XXXXXX	XX (XX.X%)	XXX	XX (XX.X%)	XXX	XX (XX.X%)	XXX

**Listing 14.2.4.2.X Listing of XXXX – Safety Set**

ID – Sex – Age	Treatment	Non-related adverse event	Start date / end date	Ongoing at the end of the study	Intensity	Serious	Action taken

**Table 14.3.1.3. Summary of incidents – Safety Set**

	Healsea Rescue N=XX		Placebo N=XX		Total N=XX	
	n (%)	[E]	n (%)	[E]	n (%)	[E]
Number and percentage of subjects with / Number of						
Incident	XX (XX.X%)	XXX	XX (XX.X%)	XXX	XX (XX.X%)	XXX
Incident leading to definitive study device discontinuation	XX (XX.X%)	XXX	XX (XX.X%)	XXX	XX (XX.X%)	XXX
Incident leading to definitive study discontinuation	XX (XX.X%)	XXX	XX (XX.X%)	XXX	XX (XX.X%)	XXX
Serious incident	XX (XX.X%)	XXX	XX (XX.X%)	XXX	XX (XX.X%)	XXX

**Table 14.3.1.4. Incidents by System Organ Class and Preferred Term – Safety Set**

SOC - Preferred Term	Healsea Rescue N=XX		Placebo N=XX		Total N=XX	
	n (%)	[E]	n (%)	[E]	n (%)	[E]
Incidents						
All	XX (XX.X%)	XXX	XX (XX.X%)	XXX	XX (XX.X%)	XXX
XXXXX						
All	XX (XX.X%)	XXX	XX (XX.X%)	XXX	XX (XX.X%)	XXX
XXXXX	XX (XX.X%)	XXX	XX (XX.X%)	XXX	XX (XX.X%)	XXX
XXXXX	XX (XX.X%)	XXX	XX (XX.X%)	XXX	XX (XX.X%)	XXX

**Listing 14.3.2.X Listing of XXXX – Safety Set**

ID – Sex – Age	Treatment	Incident	Start date / end date	Ongoing at the end of the study	Intensity	Serious	Action taken	Causality

### 13.3. WURSS-21 questionnaire – Daily symptom report

Please complete the WURSS -21 in **the evening**, taking in account the symptoms from the morning to the evening, until you do not feel sick during two consecutive days (first question ticked NO during 2 consecutive days). In the case you already ticked “not sick” for 2 consecutive days during the TREATMENT PERIOD (D1 to Day 8), please do not complete the questionnaire either.

Please fill in one circle for each of the following items:

	Not sick 0	Very mildly		Mildly		Moderately		Severely	
	0	1	2	3	4	5	6	7	
How sick do you feel today?	0	0	0	0	0	0	0	0	0

Please rate the **average severity of your cold symptoms over the last 24 hours** for each symptom:

	Do not have this symptom 0	Very mild		Mild		Moderate		Severe	
	0	1	2	3	4	5	6	7	
Runny nose	0	0	0	0	0	0	0	0	0
Plugged nose	0	0	0	0	0	0	0	0	0
Sneezing	0	0	0	0	0	0	0	0	0
Sore throat	0	0	0	0	0	0	0	0	0
Scratchy throat	0	0	0	0	0	0	0	0	0
Cough	0	0	0	0	0	0	0	0	0
Hoarseness	0	0	0	0	0	0	0	0	0
Head congestion	0	0	0	0	0	0	0	0	0
Chest congestion	0	0	0	0	0	0	0	0	0
Feeling tired	0	0	0	0	0	0	0	0	0

Over the last 24 hours, how much has your cold interfered with your ability to:

	Not at all 0	Very mildly		Mildly		Moderately		Severely	
	0	1	2	3	4	5	6	7	
Think clearly	0	0	0	0	0	0	0	0	0
Sleep well	0	0	0	0	0	0	0	0	0
Breathe easily	0	0	0	0	0	0	0	0	0
Walk, climb stairs, exercise	0	0	0	0	0	0	0	0	0
Accomplish daily activities	0	0	0	0	0	0	0	0	0
Work outside the home	0	0	0	0	0	0	0	0	0
Work inside the home	0	0	0	0	0	0	0	0	0
Interact with others	0	0	0	0	0	0	0	0	0

Live your personal life	0	0	0	0	0	0	0	0
-------------------------	---	---	---	---	---	---	---	---

**Compared to yesterday, I feel that my cold is...**

Very much better	Somewhat better	A little better	The same	A little worse	Somewhat worse	Very much worse
0	0	0	0	0	0	0

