#### 7.1.3 Primary Endpoint with methods and timing for assessing recording and analysing variables

**The AUC of Wisconsin Upper Respiratory Symptom Survey (WURSS-21) during first 8 days of symptoms will be compared between both groups.**

WURSS-21 is a validated 3-dimensional structure questionnaire [12]. This survey has been demonstrated to be responsive, and valid to assessing the severity and functional impact of the common cold. It includes 10 items assessing symptoms (symptoms score, (items 2 to 11), 9 items assessing functional impairments (quality of life score, (items 12 to 20).) and 2 items assessing respectively global severity and global change. Brown et al. [13] support the practice of using, for AUC computation, a simply summed daily global illness severity score to represent the overall symptomatic and functional impairments arising from acute upper respiratory infection.

The WURSS-21 will be assessed in an e-diary once daily in the evening, taking into account the symptoms from the morning to the evening, during D2-D8 (day of the end of treatment). At D1, the WURSS-21 will be completed during the visit. After D8, the WURSS-21 will be assessed once daily until the subject feels not sick for two consecutive days.

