**D1-D8 (at home):**

The patient will be asked to complete the electronic diary daily (WURSS-21 assessed once daily in the evening, taking into account the symptoms from the morning to the evening, adverse events/incidents/expected undesirable side effects and concomitant medications).

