## 10. EFFICACY

### 10.1. Analysis of the primary efficacy criterion

The primary objective will be analysed by performing a t-test (or a Wilcoxon test if the normality assumption is not acceptable) on the means of AUC of total WURSS-21 score during first eight days of symptoms between treatment groups.

The answers of the twenty first items of the WURSS-21 questionnaire are scored from 0 to 7 (0: negative answer; from 1 to 7: positive answer with an increasing severity level). See the daily symptom report in appendix (§13.3).

The total WURSS-21 score at each time point is the sum of the scores of the twenty first items of the WURSS-21 questionnaire:

$$\text{At each time point } t: \text{WURSS}_{\text{TOT}}(t) = \sum_{j \in \{1; \dots; 20\}} \text{WURSS}_j(t)$$

AUC of total WURSS-21 score will be computed by the method described in §6.4.7.

At time points the questionnaire has been completed, possible unanswered items will be imputed by the method described in §6.4.6.

Subjects will be analysed on the Full Analysis Set and the Per-Protocol Set. In each case, boxplots of the AUC on total score will be realized by treatment group. The number of available data and the p-value will be printed on the figure.

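### The primary questionnaire carries two recall windows, morning to evening and the last 24 hours, and neither document says which one governs

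*SAP*

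**What the plan says.** The header of the questionnaire page (SAP 13.3) asks for evening completion, "taking in account the symptoms from the morning to the evening". Below it, on the same page:

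- Item 1 asks how sick the patient feels today.
- The stem for items 2–11 asks for the "average severity of your cold symptoms over the last 24 hours".
- The stem for items 12–20, which include the *Sleep well* item, begins "Over the last 24 hours, how much has your cold interfered with your ability to".

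The protocol gives only the daytime window. Section 7.1.3 has the questionnaire assessed "once daily in the evening, taking into account the symptoms from the morning to the evening, during D2-D8". Section 7.4.1, under the D1–D8 at-home procedures, says "WURSS-21 assessed once daily in the evening, taking into account the symptoms from the morning to the evening". The baseline entry has a separate rule in 7.1.3: "At D1, the WURSS-21 will be completed during the visit".

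On scoring, SAP 10.1 states: "The answers of the twenty first items of the WURSS-21 questionnaire are scored from 0 to 7". These 20 items are summed to give the daily total, and the trapezoidal AUC of that total from D1 to D8 (SAP 6.4.7) is the primary endpoint. Items 12–20 alone form the quality-of-life sub-score (SAP 10.2.1).

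**The concern.** An evening entry cannot both leave out and include the night before. A patient who follows the header rates the waking day; a patient who follows the stems also rates the night. Nothing in either document ranks the two instructions, so two patients with the same illness can give different answers in good faith.

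The conflict lies in the instrument behind the primary endpoint, and it bears most on what happens at night, such as a blocked nose, cough or poor sleep. *Sleep well* is the clearest case, because an ordinary night's sleep falls outside a morning-to-evening window.

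The SAP 10.2.2 durations are exposed too. There a day counts as symptomatic on any answer other than the negative one, so a symptom present only at night makes the day symptomatic under the stems but not under the header.

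At stake are the precision of the primary comparison and a clear statement of what the score measures.

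**Working it through.** This is mainly a comparison of texts. The arithmetic shows how much of the score the conflict touches, not how much harm it does.

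**1. The windows side by side**

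| Place | Applies to | Window | Previous night included? |
|---|---|---|---|
| SAP 13.3, header | whole page | morning to evening | no |
| SAP 13.3, item 1 | item 1 | today | unclear |
| SAP 13.3, stem | items 2–11 | last 24 hours | yes |
| SAP 13.3, stem | items 12–20 | last 24 hours | yes |
| Protocol 7.1.3 | WURSS-21, D2–D8 | morning to evening | no |
| Protocol 7.4.1, at home | WURSS-21, D1–D8 | morning to evening | no |
| Protocol 7.1.3 | WURSS-21, D1 | at the visit; no window stated | not stated |

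No row refers to another or sets an order of precedence.

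**2. How much of the score carries a 24-hour stem** (inputs from SAP 10.1, 10.2.1 and 6.4.7)

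- Items 2–11 and 12–20: 10 + 9 = 19 of 20 items, or 19 × 7 = 133 of 20 × 7 = 140 daily points (95%).
- *Sleep well*: 7 / 140 = 5.0% of the daily maximum.
- Maximum AUC over the seven one-day intervals: 140 × 7 = 980. *Sleep well* contributes at most 7 × 7 = 49, and 49 / 980 = 5.0%.
- Quality-of-life sub-score: 9 × 7 = 63 points. *Sleep well* is 7 / 63 = 11.1%.

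**3. D1.** The first entry is made on site after randomization, so a morning-to-evening window would stop at the visit, whereas the 24-hour stem can be applied there as on any other day. In the trapezoidal rule D1 has weight 0.5 out of 7, or 7.1%. The first spray is used that evening (Protocol 7.4.1), so D1 precedes treatment.

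**4. Illustration of the effect on power.** The planned 180 cannot be reproduced, because no standard deviation is given; the dropout step can be: 180 / (1 − 0.10) = 200. Solving backwards with 90 per group, one-sided 0.05, 80% power and the normal approximation:

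- standardised difference = (1.645 + 0.842) × √(2/90) = 0.371
- implied coefficient of variation = 0.30 / 0.371 = 0.81

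That value is inferred, not stated. If the ambiguity inflated the AUC variance by an assumed amount and left the mean difference unchanged:

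| Assumed extra variance | Power |
|---|---|
| 0% | 80% |
| 1% | 79.7% |
| 5% | 78.3% |
| 10% | 76.6% |

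Nothing in the documents says where in this range, or outside it, the true value lies.

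**The case against.** The best defence has four parts.

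- **The stems are the more specific instruction.** They sit directly above their items, and the header can be read as asking for the whole day rather than the present moment. That is a reasonable reading, but the documents do not state it, and the protocol gives only the daytime window.
- **The header speaks of symptoms.** Items 12–20 ask about interference with function, so read literally the header does not reach *Sleep well*. This has some force. However, both protocol sections apply the daytime window to the WURSS-21 as a whole. Even on the narrow reading, items 2–11 remain in conflict: 10 × 7 = 70 of 140 points.
- **Training is central.** There is one site, staff go through the questions at Visit 1, and the first questionnaire is completed there. This makes wide variation between patients less likely, but the plan does not say which window staff are to teach.
- **D1 has its own rule.** Section 7.1.3 limits the daytime window to D2–D8, and D1 is before treatment in both randomised arms. So D1 is a minor point, though section 7.4.1 and the SAP header do not repeat the limit.

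Some stronger inferences are tempting, but the documents do not support them:

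- That night-time symptoms or *Sleep well* go unscored. *Sleep well* is printed under its own 24-hour stem and summed, and if left blank on a completed page it is carried forward (SAP 6.4.6).
- That the header overrides the stems, or that the scores depart from the validated form. Protocol 7.1.3 calls the instrument validated but does not say with which recall window.
- That a night-time treatment effect is lost. Neither document predicts one.
- That SAP section 12, where patients who no longer felt sick still reported symptoms, shows the mixed windows at work. That is one possible explanation and mild residual symptoms are another; the cause is not established.

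**Conclusion.** The contradiction is certain as a matter of text: two incompatible windows, one page, no rule of precedence, and 19 of the 20 items in the primary score carrying the 24-hour stem. It is worth correcting because it concerns the primary instrument and the correction is simple.

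The harm is less certain and probably small. The page is the same in both blinded arms, so the expected effect is extra noise and a less clear construct, not a directional bias. The 95%, 5.0% and 11.1% figures are item weights and must not be read as measured error. The power figures rest on an inferred coefficient of variation of 0.81 and assumed variance inflation of 1–10%. The documents give neither the share of patients following each instruction nor the size of night-time symptoms. The quality-of-life sub-score is in any case descriptive under SAP 6.3.1.

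One assumption underlies this: that the e-diary shows the same wording as the page in SAP 13.3.

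**What to change.** Delete the morning-to-evening clause from Protocol 7.1.3, from the at-home paragraph of Protocol 7.4.1, and from the header in SAP 13.3 and the e-diary. Keep evening completion at home, and let the 24-hour stems define recall for items 2–20 at every time point, including the D1 entry on site. Staff instruction at Visit 1 should use the same window. The cost is a short protocol amendment and an update to the e-diary text, with no new data and no extra burden on patients.

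The past tense in SAP section 12 suggests that diaries were already being reviewed when it was written. A change of wording cannot repair entries already made. In that case, the report should quote the wording that patients actually saw and state the mixed recall window as a limitation. A quality-of-life AUC without *Sleep well* can be added as an optional, descriptive table. It changes the defined nine-item score and leaves the other 18 items with a 24-hour stem as they are, so it should not be presented as a correction.
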